6.1.1 Description of Intervention

The original treatment manual includes eight weekly sessions focusing on tobacco use and PTSD psychoeducation, behavioral coaching tailored for smokers with PTSD, scheduling a quit date in Session 5, and providing skills for relapse prevention. PTSD-specific skills include: controlled breathing, coping plans to manage trauma-related triggers, and strategies to manage anxiety sensitivity, emotional numbing, and low mood (see Figure 4). Consistent with the office-based manual, sessions will occur weekly, with identical duration to the original IC protocol (20-30 minutes per session), and will include use of a modified workbook tailored to the manual. Telephone sessions will be scheduled weekly and phone calls will occur proactively (therapist calls participant). The content of the revised manual and workbook will be thematically similar in approach, topic areas, and content to the officebased manual, but will be revised to include: (1) an interactive question-and-answer format aimed at engaging the participant more actively during telephone sessions; (2) prompts instructing participants to access the workbook at the beginning and end of sessions to minimize interruptions; and (3) prompts directing the participant to utilize the SQC app and iCO Smokerlyzer. SQC app will be populated with personalized information such as reasons for quitting, a coping plan for managing PTSD and smoking triggers, and a medication plan. The iCO Smokerlyzer enables participants to test their breath CO level anywhere and download the readings to their smartphones for review during telephone counseling sessions.

Session	Week	Core Content of Eight Intervention Sessions
1	1	Assess nicotine dependence, identify reasons for quitting, encourage med adherence if prescribed meds; introduce behavioral plan to reduce cigarette use; reinforce SQC app and iCO use
2	2	Set quit date, identify smoking triggers and PTSD symptoms related to smoking; introduce controlled breathing and coping plans for triggers and PTSD symptoms; reinforce SQC app and iCO use
3	3	Review assignment to practice coping with smoking triggers and PTSD symptoms, develop action plan to manage triggers and

		symptoms, assess adherence with medications; reinforce SQC app and iCO use
4	4	Implement behavior changes to prepare for quit date while managing PTSD symptoms; reinforce SQC, iCO use

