5 (Quit Week)	5	Review assignment to practice coping with smoking triggers and PTSD symptoms, develop action plan for quit date, introduce relapse prevention; coordinate with prescriber reinforce SQC app and iCO use
6	6	Reinforce coping plans, SQC app and iCO use, controlled breathing, adherence with medications
7	7	Assess for PTSD symptom exacerbations associated with cigarette reduction and/ or cessation
8	8	For non-abstinent patients: reset quit date, reinstate appropriate treatment

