cigarette or non-cigarette tobacco on any of the seven and 30 consecutive days prior to the assessment, respectively; and (2) salivary cotinine levels < 10 nanograms/milliliter.⁸⁶ For participants using NRT and for those who reported use of smokeless tobacco, e-cigarettes during the study, abstinence status will be independently verified by a friend or family member. Participants with missing salivary cotinine or those unable to obtain verification from a friend or family member will be considered non-abstinent. Participants will be provided with postage-paid mailers, a collection kit, and detailed instructions for saliva collection and will be asked to collect specimens, store them in their home freezer, and mail them to our lab, where they will be batch shipped on dry ice to the Salimetrics lab for analysis.

- · Nicotine dependence: We will administer the FTND at Weeks 0, 8, 12, and 24.
- PTSD symptoms: We will administer the PCL-5 at Weeks 0, 8, 12, and 24.

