Treatment Fidelity: Fidelity maintenance (1) ensures that the treatment delivered is the treatment intended, thereby safeguarding internal validity, (2) minimizes the influence of therapist effects, 80 and (3) facilitates dissemination and implementation by providing training programs and quality assurance procedures. Treatment fidelity ratings are a critical part of adherence to CONSORT guidelines as applied to psychosocial interventions. 81 Adherence to the treatment model, which is improved through fidelity maintenance procedures, is associated with improved outcomes in both research and clinical implementation. 82,83 The therapist will undergo a two-hour initial training with the PI, who is well-versed at delivering the original IC protocol. The therapist will then will attend a weekly supervision meeting with the PI. We will ensure a minimum of one hour of supervision per week for every four cases. Treatment sessions will be audiotaped using a telephone recording device that allows both sides of the conversation to be recorded. The PI will randomly select 10% percent of the audiotapes for adherence ratings by research clinical evaluators. This type of intensive

supervision will ensure therapist fidelity,⁸⁰ thereby minimizing threats of the internal validity of the study.

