Control condition: Consistent with the current standard of care in VA clinics in rural areas, controls will be referred to the proactive VA Telephone QL. 55,84 Participants will receive instructions to call the VA QL 55,84 in Week 1 and will then request to receive weekly proactive telephone calls thereafter. They will be asked to track their weekly participation in QL sessions and duration of each session and will be instructed to request follow up calls weekly from the QL counselor for up to seven weeks thereafter (eight total). We selected the VA QL as a control because it accurately represents real-world treatment provided to veterans in VA settings, particularly in rural areas. The VA QL is a national toll-free number available to veterans that allows them to speak with a smoking cessation counselor for as many weekly sessions as needed (minimum recommended five sessions, more as needed) to develop a quit plan and receive counseling, strategies to prevent relapse, and weekly proactive follow-up calls based on National Cancer Institute guidelines. Sessions provide evidence-based smoking cessation counseling, but no resources or skills to manage mental health symptoms, such as PTSD symptoms, are provided.

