6.3.4 Recruitment, Enrollment and Retention6.3.5 On Study VisitsMEDICATION MANAGEMENT

Initial visit: The PI will meet with each participant at baseline (Week 0) prior to randomization to prescribe NRT (patch, gum, and/or lozenge) if desired, following a VA prescribing algorithm consistent with current prescribing guidelines.12,79 The session will be either in-person or through the telemedicine (V-tel) clinical services at the SFVAMC CBOCs. NRT will follow standard VA prescribing guidelines and will be based on (1) safety, (2) nicotine dependence level, and (3) participant preference. All participants will be instructed to set a goal of stopping cigarette, e-cigarette, and smokeless tobacco use during the course of study.

NRT monitoring: Following the initial visit, a study psychiatrist who is blinded to group assignment will contact participants in both conditions once monthly by phone to monitor for NRT side effects, adjust dosing, and renew refills. Participants who decline NRT will also receive a brief monthly check-in call to eliminate any potential therapeutic effect of these calls on study outcomes. All participants will remain on NRT as long as is clinically indicated throughout the 24-week study period, as determined by the study psychiatrist. Participants may contact the psychiatrist with any side effects or concerns related to NRT.

STUDY INTERVENTION PERIOD

Intervention condition: Details on the weekly telephone counseling sessions are provided in Section 6.1.4. Study therapists will conduct the sessions from private offices at SFVAMC, and veterans will participate via phone from their home or other location that is convenient for the.

Control condition: Details on the QL control condition are also provided in Section 6.1.4. QL sessions are also conducted via phone, and veterans will participate, as frequently as desired, from their home or other location that is convenient for the.

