6.3.7 Removal of Subjects

Rules for Withdrawing Study Participants from the Study Interventions: Participants will be withdrawn from the study if, in the opinion of the DSMB or the PI, there is: sustained clinically significant worsening of symptoms, unacceptable adverse events judged to be related to study interventions, or any other clinically significant medical (e.g., pregnancy), psychiatric, or substance-use related poor outcome that makes continued study participation unsafe in the clinical judgment of the PI or DSMB members.

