7.10 Study Discontinuation

The study would be discontinued in the following circumstances:

- 1. Risks of participation are determined to greatly exceed potential benefits; or
- 2. Risk of participation in one arm of the study is determined to greatly outweigh that of the other.

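### Before Week 8, PTSD worsening is actively elicited only in the intervention arm, while the withdrawal and arm-versus-arm discontinuation rules span both arms and name no data source

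*Combined protocol and SAP*

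**What the plan says.** All references are to the combined protocol and SAP.

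- **Intervention sessions (6.1.1).** Session 2 (Week 2) is to "identify smoking triggers and PTSD symptoms related to smoking". Sessions 3 to 5 continue work on PTSD symptoms. Session 7 (Week 7) is to "Assess for PTSD symptom exacerbations associated with cigarette reduction and/ or cessation". Under 6.1.4 the therapist will "attend a weekly supervision meeting with the PI".
- **Control counselling (6.1.4).** Controls use the external VA Quitline, where "no resources or skills to manage mental health symptoms, such as PTSD symptoms, are provided".
- **Study contact with controls (6.1.3, Aim 2).** The study team contacts each control weekly to ask about that week's Quitline session and its length.
- **Monthly call (6.3.5, NRT monitoring).** A psychiatrist blinded to assignment will "contact participants in both conditions once monthly by phone to monitor for NRT side effects, adjust dosing, and renew refills". Those who decline NRT are called too.
- **PTSD measure (6.1.3).** "PTSD symptoms: We will administer the PCL-5 at Weeks 0, 8, 12, and 24", with no restriction to one arm.
- **Adverse events (6.2.2.1).** Participants are monitored for new events at every visit and telephone contact. The definition includes a baseline condition that becomes worse.
- **Decision rules.** Section 6.3.7, repeated in 7.8, withdraws a participant for, among other things, "sustained clinically significant worsening of symptoms", as judged by the PI or DSMB. Section 7.10 discontinues the study if "Risk of participation in one arm of the study is determined to greatly outweigh that of the other". Neither names an instrument or data source.

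**The concern.** Section 7.1 names exacerbation of PTSD symptoms as a risk of participation, so it is an event on which the arms could be compared. In one arm a trained therapist raises PTSD symptoms as part of treatment and meets weekly with the PI, who is one of the people deciding on withdrawal. In the other arm the counsellor is outside the study and gives no PTSD support, and the study's own calls have other stated purposes.

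With equal true risk, the arm that is asked more reports more. Two things would then be at stake:

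- **The safety comparison.** Under 7.8 the DSMB receives adverse events, and 7.10 rests on relative risk between arms. Better detection in the intervention arm could be read as greater harm there, while worsening in controls would be the less visible risk.
- **The outcomes.** Study completion is a feasibility outcome (5.2.1), and 6.3.1 lists sessions completed as a primary outcome. A withdrawal that follows from better detection would count against the intervention on both. Each one is 1/40 = 2.5 percentage points of an arm.

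**Working it through.** The plan states no figure on this point, so there is none to reproduce. The check sets the two arms side by side and then illustrates the possible size.

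**Step 1. What is scheduled after baseline and before the Week 8 PCL-5**

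| | Intervention | Control |
|---|---|---|
| Weekly contact | Therapy session with PTSD content from Week 2 (6.1.1) | Study call about Quitline attendance (6.1.3) |
| Scheduled PTSD exacerbation check | Week 7 (6.1.1) | None |
| Weekly route from counsellor to PI | Yes (6.1.4) | None stated; counsellor is external |
| Monthly blinded psychiatrist call | Yes, for NRT (6.3.5) | Yes, for NRT (6.3.5) |
| General adverse event monitoring | Every contact (6.2.2.1) | Every contact (6.2.2.1) |

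Contact frequency is similar: about eight weekly contacts in each arm, plus about one monthly call before Week 8 (near Week 4, if calls run every four weeks from Week 0). What differs is content. Scheduled PTSD-specific checks number at least one in the intervention arm and none in controls.

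**Step 2. How far ahead the Session 7 check runs.** Week 8 minus Week 7 is one week. Session 7 alone is therefore a small lead over the common PCL-5. The asymmetry rests mainly on the PTSD content from Week 2 and the weekly supervision.

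**Step 3. Illustrative size.** From the plan: n = 40 per arm. Assumed, because the documents give neither: the true proportion worsening, p, equal in both arms, and the detection probabilities s_I (intervention) and s_C (control).

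Expected detected cases = n × p × s. Spurious excess = n × p × (s_I − s_C).

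With p = 0.20, 40 × 0.20 = 8 participants worsen in each arm. With s_I = 0.90:

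| s_C | Intervention | Control | Excess | Ratio |
|---|---|---|---|---|
| 0.90 | 8 × 0.90 = 7.2 | 8 × 0.90 = 7.2 | 0 | 1.0 |
| 0.70 | 7.2 | 8 × 0.70 = 5.6 | 1.6 | 1.3 |
| 0.50 | 7.2 | 8 × 0.50 = 4.0 | 3.2 | 1.8 |
| 0.30 | 7.2 | 8 × 0.30 = 2.4 | 4.8 | 3.0 |

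Over the same range of s_C, the excess is 0 to 40 × 0.10 × 0.60 = 2.4 cases at p = 0.10, and 0 to 40 × 0.30 × 0.60 = 7.2 at p = 0.30.

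**Step 4. Would such a gap stand out?** Rounded to whole cases, 7 of 40 against 4 of 40 gives a two-sided Fisher p of 0.52, and 7 against 6 gives 1.0. Neither would be convincing in a formal test. Section 7.10, however, specifies no test, so a DSMB may well be looking at raw counts.

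**The case against.** The strongest case on the other side has five parts.

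- **Controls are not unobserved.** A reader might infer that their worsening goes unseen until Week 8. The documents do not support that. Controls have weekly study contact, monthly calls from a blinded psychiatrist, and adverse event monitoring at each contact under a definition that covers aggravated baseline conditions. They also have emergency contacts and access to mental health care (7.1). A detection route exists; what is missing is a stated PTSD question on it.
- **Session 7 is treatment content, not a safety instrument.** A reader might infer that its findings feed withdrawal or discontinuation and so produce more of both in the intervention arm. Nothing in the documents says so. Section 6.3.7 needs sustained worsening and clinical judgment, and 7.10 needs a large imbalance. This objection stands against a claim of demonstrated harm. It does not remove the gap, because nothing excludes those findings either and monitoring covers every telephone contact.
- **A symmetric measure exists.** The PCL-5 is taken on one schedule in both arms, and the DSMB also sees important exploratory measures. This gives an equal basis from Week 8 on, but 7.10 does not name it as the basis and says nothing about earlier events.
- **The size is assumed.** This stands. With equal detection the excess is zero.
- **The comparator is deliberate, this is a pilot, and safety is not a primary outcome (6.2.2).** These points limit the weight of the concern. In addition, the separate schedule of measures cited in 6.3.1 is not part of the text reviewed, so it might specify further questions.

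**Conclusion.** The point holds as one of unequal ascertainment. As written, PTSD worsening before Week 8 is actively elicited in the intervention arm and reaches the study in controls only through general adverse event monitoring on calls made for other purposes. Two rules that span the arms do not say which data they use. The likely direction is to make the intervention look riskier.

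The size cannot be determined from the documents. Under the assumptions shown (20% truly worsening in each arm, detection 90% against 30% to 90%) it is 0 to 4.8 excess detected cases of 40. The documents show neither that control worsening would be missed altogether nor that either rule would be triggered wrongly. This is a cheap improvement to the comparability of safety data, not a flaw that invalidates the trial.

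**What to change.** 1. Ask one brief, identical adverse event item set, including PTSD worsening, in both arms at contacts that already exist. Use the monthly blinded psychiatrist call, and also the weekly study contact with controls, matched by the same items at the weekly intervention session. The monthly call alone is not enough: it gives about one check before Week 8, and near Week 4 that check would precede the intervention's Week 5 quit week.
2. Base the between-arm safety tables for the DSMB on those common items plus the PCL-5. List events elicited only through therapy content separately. Report completed contacts by arm, so that the opportunity to report is visible. The blinded call is the cleaner source, because the weekly items would be asked by different people in the two arms.
3. The sponsor should reconcile 6.1.1, 6.2.2.1, 6.3.5, 6.3.7 and 7.10 on the source of PTSD-worsening data. No threshold, withdrawal criterion or other clinical rule is proposed here.

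The cost is a few minutes per existing call and one short form, with no new visit or staff.

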6.1.2 Method of Assignment/Randomization

Eligible participants will be randomized to one of two conditions (intervention or control condition) in a 1:1 ratio according to a computer-generated code provided by the study biostatistician.

6.1.3 Selection of Instruments/Outcome Measures

Aim 1: Feasibility and Acceptability of the Intervention

- · Feasibility: We will calculate the: a) proportion of those eligible among those screened in rural and urban areas; b) proportion enrolled among those eligible; c) the rate of enrollment; d) adherence to medications (percentage of days participant takes NRT of total days prescribed); e) total number of sessions completed in each condition; f) iCO and SQC app usage data (intervention participants only); and g) study completion rate. To assess NRT adherence and estimate app usage data, participants will be asked to record daily medication adherence in a paper log using the TLFB method with specific anchor dates in a calendar, which will be mailed to the study team at each assessment time point. Pharmacy refill data will be reviewed at each time point to confirm TLFB self-report of medication adherence.
- · Qualitative Interview (Acceptability): We will conduct a 20-minute semi-structured, audiorecorded telephone interview at Week 8 with intervention condition participants only to

collect in-depth feedback about user satisfaction with features of the overall intervention and its components (telephone sessions, SQC app, iCO monitor). We will use a framework of open-ended questions based on an interview guide developed by the study team, similar to that used in the focus groups with the CAP (see 3B.4), but with a greater emphasis on the acceptability of the intervention and its individual components (telephone sessions, SQC app, iCO monitor) in a therapeutic context during a quit attempt. We will inquire about individual features of each component of the intervention and perceived helpfulness; feasibility and acceptability in rural and urban settings; acceptability of the intervention in a military/ veteran cultural context; anticipated barriers and facilitators of implementation; the balance of adequate therapeutic intervention versus time burden; scheduling; cost-effectiveness; and issues of mobile device accessibility and connectivity. Audio-recordings of the interviews will be transcribed and relevant portions about acceptability of the intervention will be noted.

- · System Usability Scale (SUS)^{72,85}: The SUS is a brief, reliable and valid instrument to measure perceptions of usability of technology devices, with higher scores reflecting greater usability (maximum score of 100). We will administer the SUS for the SQC app and iCO monitor at Weeks 8, 12 and 24 follow-ups in the intervention condition only.
- · Acceptability questionnaires: Participants will complete a questionnaire developed by our team to rate the protocol from 1-10 in the following areas: perceived helpfulness, understandability, and likelihood of use at Weeks 8, 12, and 24 follow-ups in the intervention condition only. The Client Satisfaction Questionnaire-8, a validated measure of client satisfaction with behavioral interventions, will also be administered. Total mobile app data usage of iCO and SQC will be recorded and participants will be asked to record usage of iCO or SQC apps daily on the TLFB paper log (see Section 3C11).

Aim 2: Retention (Attendance)

We will record attendance at each weekly session in both conditions during the eight-week study period. For intervention participants, the study team will document attendance and duration of each visit (target 20-30 minutes). For control participants, the study team will contact participants once weekly and inquire about their participation in the QL session for that week and estimate the number of minutes in each QL session. Per VA guidelines, intervention participants will receive a reminder call the day before each weekly appointment and will receive three outreach calls after a missed appointment before the visit is considered a no-show. Rescheduled appointments must be completed within the week of the originally scheduled visit; those that are not will be considered a no-show. Patients who decide to stop treatment or stop attending treatment in both conditions will be invited to complete follow-up assessments.

Exploratory Aims: Tobacco Use and PTSD Symptoms

Use of cigarette, e-cigarette, and chewing tobacco: We will use the TLFB method to record use of nonprescribed nicotine and tobacco products for past 30 days at Week 0 (baseline) and at Weeks 8, 12, and 24.⁷¹ Seven-day and 30-day point prevalence abstinence will be assessed at 12 weeks and 24 weeks and will be defined as (1) no smoking and no use of e-

cigarette or non-cigarette tobacco on any of the seven and 30 consecutive days prior to the assessment, respectively; and (2) salivary cotinine levels < 10 nanograms/milliliter.⁸⁶ For participants using NRT and for those who reported use of smokeless tobacco, e-cigarettes during the study, abstinence status will be independently verified by a friend or family member. Participants with missing salivary cotinine or those unable to obtain verification from a friend or family member will be considered non-abstinent. Participants will be provided with postage-paid mailers, a collection kit, and detailed instructions for saliva collection and will be asked to collect specimens, store them in their home freezer, and mail them to our lab, where they will be batch shipped on dry ice to the Salimetrics lab for analysis.

- · Nicotine dependence: We will administer the FTND at Weeks 0, 8, 12, and 24.
- PTSD symptoms: We will administer the PCL-5 at Weeks 0, 8, 12, and 24.

